8.10 Statistical Software

All statistical analyses will be performed with SAS[®], Version 9.4 or later. Working instructions are printed in yellow italic text below the shells, e.g.: *Repeat table for PPS (14.2.2)*.

Sponsor Name: Navitas Life
 Sciences GmbH
 Statistical Analysis Plan (SAP)
 Version No.: Final 1

Short Title of Study: Long-Term Retention of
 Gadolinium in Bone
 Sponsor Study No.: ALS-Gd64/001
 Date: 31JUL2019
 NLS Study No.: 665

9 STATISTICAL ANALYSES

The statistical analysis will be carried out for all GBCA groups pooled as well as each GBCA group separately and the control group. They will be further stratified according to renal function category (2 groups), single / multiple doses (2 groups), and the combination of “renal function with “single / multiple doses”.

All tables will be programmed for the control group, all GBCA groups pooled as well as for each GBCA group separately. Each table will be presents by all stratification for the renal function categories (2 groups = 2 columns). Repeat tables will be produced by treatment/renal function and dose (single / multiple doses) combined.

Because standard point estimates may be biased when the total number of BLQ values is large (such as when it exceeds 1/3 of the total), the descriptive analysis should only to be calculated if at least 2/3 of the individual data had been measured and found to be above the LLOQ (rationale based on PhUSE_CSS_WhitePaper_PK_final_25March2014.pdf).

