### 3.1 Discussion of study design

The current study design is explorative in nature and will deliver descriptive data on the potential for long-term retention of gadolinium in human bone. Restricting the study population to patients with stable normal renal function is unlikely to provide further insight into the mechanism of Gd retention and the potential development of NSF. Therefore, subgroups with different degrees of renal decrement are included.

A limitation of the study is the retrospective nature of data associated with the single or multiple administration of the GdCAs. It is anticipated that some of the specified analytical clinical and laboratory parameters will not be available within the patient records. However, it would be impossible to prospectively assess potential Gd retention in patients with moderate and

severe decrement in renal function, because the administration of GdCAs to such patients is now limited due to regulation.

The current study, therefore, will enrol patients who received a specified GdCA at least 1 month prior to an orthopaedic surgery procedure and will prospectively collect bone and skin samples for analysis. Conducting the study in patients who plan to undergo a medically indicated orthopaedic surgery procedure provides an accessible model for collecting samples without adding a significant interventional load onto the patients. The collection of bone and skin biopsies are required to correlate Gd content in bone and skin with potential histopathological findings associated with NSF.

GdCA-naïve patients will be included as controls for any background concentration of Gd in bone, e.g. from the environment. For example, Gd has been found in skin biopsies of NSF patients who were considered to be “gadolinium-free” (23), as well as in bone samples from patients with no previous exposure to GdCA (21).

In summary, the study design is adequately selected to contribute to the understanding of long-term Gd retention in patients who receive GdCAs. The study design was developed through scientific discussions with the EMA/ CHMP.

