8.1 Descriptive Statistics

The following descriptive statistics will be calculated for continuous data and for ordered categorical data (ordinal data) if applicable:

Summary statistics are displayed with the following digits:

Description	Characteristic	Number of decimal places
Count	n	0
N (number of non-missing measurements)	N	0
Arithmetic Mean	Mean	As in source + 1
Geometric Mean	GM	As in source + 1
Standard Deviation	SD	As in source + 1
Geometric standard deviation	GSD	As in source + 1
Corresponding %CV	%CV	2
Minimum	Min	As in source
Median	Median	As in source + 1
Maximum	Max	As in source
Percentage relative to N	%	1 *

Sponsor Name: Navitas Life Sciences GmbH
 Statistical Analysis Plan (SAP)
 Version No.: Final 1

Short Title of Study: Long-Term Retention of Gadolinium in Bone
 Sponsor Study No.: ALS-Gd64/001
 Date: 31JUL2019
 NLS Study No.: 665

* Number of decimal places can be two, if necessary. All table percentages should be rounded to one decimal place if not stated otherwise. If the rounded percentage is 0.0%, then the percentage should be printed as < 0.1%.

For ordered categorical data and nominal data, absolute and relative frequencies (in %) will be calculated. A Missing category should be added to any parameter for which information is not available for any subjects and included in all calculations (%).

All relevant medical history conditions and concomitant diseases will be coded in MedDRA and summarized by system organ class and preferred term. The version of the utilized dictionary will be presented as part of the provided tables and listings.

Any disease starting at the date of informed consents or later will be classified as concomitant disease.

All prior and/or concomitant medications and therapies will be coded according to the World Health Organization (WHO) Drug Dictionary according to WHO Preferred Term (ATC level 5). Subjects taking the same medication multiple times will be counted once per medication. The version of the utilized dictionary will be presented as part of the provided tables and listings.

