All medication and therapies starting at the date of informed consents (IFC) or later will be classified as concomitant medications and concomitant therapies, whereas, all concomitant medications and therapies starting before the date of IFC will be classified as previous medications and previous therapies. Any previous medications or previous therapies that is still ongoing will be classified as both prior and concomitant medications and prior and concomitant therapies.

All AEs will be presented by primary system organ class and preferred term and sorted alphabetically if not stated otherwise.

All data will be presented in the subject data listings.

If either table or listing does not include any observation, then the following placeholder will be used: "NO DATA CONTRIBUTED TO THIS TABLE / LISTING".

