8.5 Data Handling

There will be no imputation of missing data. All data will be analyzed as they appear in the data base.

Since the geometric mean (the retransformed mean of the logarithmized values) and CV% cannot be calculated in the presence of zero values, the values BLQ were implemented in the IA analysis by half the LLOQ (i.e. 0.025) instead of zero for the calculation of the descriptive statistics. This approach will also be

Sponsor Name: Navitas Life
 Sciences GmbH
 Statistical Analysis Plan (SAP)
 Version No.: Final 1

Short Title of Study: Long-Term Retention of
 Gadolinium in Bone
 Sponsor Study No.: ALS-Gd64/001
 Date: 31JUL2019
 NLS Study No.: 665

used for the final analysis. Therefore, values below the limit of quantification (LLOQ) will be replaced by half of the LLOQ (i.e 0.025) instead of zero for the calculation of the descriptive statistics. For adverse events the following rules will be applied:

- AEs with unknown onset date/time will be counted as treatment emergent AEs.
- AEs with unknown end date/time will be counted as an ongoing AE.
- AEs with unknown relationship to GBCA will be counted as related in AE summary tables.
- If for the calculation of a time period the full date format ddmmmyyyy is needed, missing entries will be imputed as follows:
 - Missing day in start date of a time period is imputed by the first day of the month;
 - Missing day in stop date of a time period is imputed by the last day of the month;
 - Missing month in start date of a time period is imputed by January of the year;
 - Missing month in stop date of a time period is imputed by December of the year;
 - Missing year is not imputed.

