9.6 Analysis

9.6.1 Primary Analysis

The primary evaluation parameters Gd concentration in bone (trabecular and cortical) will be descriptively tabulated for the control group and each of the 6 GBCAs (Gadobutrol, Gadodiamide, Gadopentetic acid, Gadoteric acid, Gadoversetamide, and Gadoxetic acid) and presented by renal function status: stable normal renal function (eGFR > 60 ml/min/1.73 m²) and at least moderate impaired renal function (<=60 ml/min/1.73 m²). For mean, SD and %CV the geometric equivalents will be calculated.

The primary analysis will be performed on the full analysis (FAS) and the per protocol set (PPS) (see definitions 8.3).

No statistical tests will be calculated.

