16 LIST OF REPORTED SUBJECT DATA LISTINGS

In general, subject data listings should include all subjects with data. The numbering of all TLFs is following the ICH guidelines.

To display all necessary subject data for the IA there was only one subject data listing created. Since this SAP will display all available data for all included subjects, there will be no equivalent listing to the IA SAP. The provided IA listing is a combination out of subject data listing 16.2.2.1, 16.2.6.1 and 16.2.6.2.

No.	Title
16.2.1	Subject Disposition
16.2.1.1	Subject Enrolled but Surgery did not take place
16.2.1.2	Subjects who Discontinued Prematurely
16.2.1.3	Subjects Applying for Interim Analysis
16.2.1.4	Protocol Violations
Preface A	List of Inclusion and Exclusion Criteria
16.2.1.5	Eligibility Criteria
16.2.2	Demographic Data and Baseline Characteristics
16.2.2.1	Demographic Characteristics
16.2.2.2	Baseline Characteristics - Diagnosis of Qualifying Study Indication
16.2.3	Medical History and Concomitant Diseases
16.2.3.1	Relevant Medical History and Concomitant Disease(S)
16.2.4	Previous and Concomitant Medication
16.2.4.1	Prior and/or Concomitant Medication and Therapy
16.2.5	Orthopedic surgery

Sponsor Name: Navitas Life
Sciences GmbH

Statistical Analysis Plan (SAP)

Version No.: Final 1

Short Title of Study: Long-Term Retention of
Gadolinium in Bone

Sponsor Study No.: ALS-Gd64/001

NLS Study No.: 665

Date: 31JUL2019

No.	Title
16.2.5.1	Bone and tissue sampling by Surgery Number
16.2.6	Analysis
16.2.6.1	Gadolinium Contrast Agent (GBCA)
16.2.6.2	Dosing Timepoints and Intervals
16.2.6.3	Vascular, Thrombotic and/or Proinflammatory Events
16.2.6.4	Concomitant Drug Treatments with Potential Impact on Bone Metabolism
16.2.6.5	Serum Concentrations
16.2.6.6	Iron Mobilization Events
16.2.6.7	Disorders Related to T4/Tsh
16.2.6.5	Erythropoietin Treatments
16.2.6.6	Histopathological evaluation of skin samples
16.2.7	Adverse Events
Preface B	Legends to Adverse Events
16.2.7.1	Adverse Events
16.2.7.2	Original Onset and End Dates and Times of Adverse Events
16.2.8	General Checks
16.2.8	General Checks by Visit
16.2.9	End of Study
16.2.9	End of Study

Sponsor Name: Navitas Life
Sciences GmbH
Statistical Analysis Plan (SAP)
Version No.: Final 1

Date: 31JUL2019

Short Title of Study: Long-Term Retention of
Gadolinium in Bone
Sponsor Study No.: ALS-Gd64/001
NLS Study No.: 665

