17 MOCKUPS OF TABLES AND SUBJECT DATA LISTINGS

Please note: Yellow resp. cursive texts are working advices.

In General:

- *Required margins: at least 1.0 cm on the upper and lower margin and at least 1.5 cm on the left and right sides. All tables and listings will be landscape and centered format. All figures will be landscape and centered format, unless portrait orientation suggests that the information presented is easier to interpret.*
- *All output should have the following header at the upper left margin:*
<Sponsor>
Protocol No.: <Protocol No.>
and the following header at the upper right margin:
<Draft/Final Version>, ddmmmyyyy
Page n of N
- *Tables/appendices/listings should be internally paginated (i.e., page numbers should appear sequentially within each table). The name of the SAS program used to generate the output shall be displayed in the lower left corner. SAS Monospace, font size 8 will be used, although the mockup below would indicate differently.*
- *Tables of Contents will be generated separately for Tables and Listings, listing numbers and titles. A file separate from Tables and Listings output must be produced. TOC pages will bear the standard header.*

Tables in general:

- *Each table will present all types of renal function in separate columns and next to each other. If necessary, add a column for total.*
- *If applicable tables will be repeated by treatment (Control, GBCA-Overall, Gadobutrol, Gadodiamide, Gadopentetic acid, Gadoteric acid, Gadoversetamide, and Gadoxetic acid) and by treatment and dose (single/multiple) separately.*

Data Listings in general:

- *All Listings should be - paged by treatment and sorted by renal function, subject and actual date and time.*

Use the appropriate table type as shown below. For more detail description refer to NLS Catalog for Mock ups to support the SAP.

Sponsor Name: Navitas Life
Sciences GmbH
Statistical Analysis Plan (SAP)
Version No.: Final 1

Date: 31JUL2019

Short Title of Study: Long-Term Retention of
Gadolinium in Bone
Sponsor Study No.: ALS-Gd64/001
NLS Study No.: 665

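### The 2/3-above-LLOQ rule in SAP 9, read as written, blanks whole primary table cells, including N, minimum, median and maximum, and no BLQ count is planned in their place

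*SAP*

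**What the plan says.** SAP 9 sets a reporting threshold for Gd summaries: "the descriptive analysis should only to be calculated if at least 2/3 of the individual data had been measured and found to be above" LLOQ. The reason it gives is that standard point estimates may be biased once BLQ values exceed about a third of the total.

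SAP 8.1 defines what is calculated ("The following descriptive statistics will be calculated for continuous data and for ordered categorical data (ordinal data) if applicable"): N, arithmetic and geometric mean, SD, geometric SD, %CV, minimum, median and maximum. Protocol 8.1.2 lists the same statistics with no threshold. SAP 10 says the SAP prevails where the two differ.

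SAP 8.5 adds that "values below the limit of quantification (LLOQ) will be replaced by half of the LLOQ (i.e 0.025) instead of zero" when the descriptive statistics are calculated, and gives no unit for that figure.

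For the primary analysis, SAP 9.6.1 says Gd in trabecular and cortical bone "will be descriptively tabulated for the control group and each of the 6 GBCAs", by renal function. SAP 17 says of the table columns: "If necessary, add a column for total".

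On individual data, SAP 8.1 says "All data will be presented in the subject data listings". No listing title in SAP 16 names tissue Gd. Its presence is inferred from SAP 8.1, SAP 17.2 and the remark that "The provided IA listing is a combination out of subject data listing 16.2.2.1, 16.2.6.1 and 16.2.6.2".

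**The concern.** The rule is wider than its reason. LLOQ/2 substitution can distort means, SDs and CVs. It cannot alter N, and it cannot alter an order statistic that was itself measured. SAP 9 nevertheless makes the whole descriptive analysis conditional and names nothing that is still shown below the threshold. BLQ handling appears only in SAP 8.5, 9 and 10.1. None of these, nor the table list (SAP 14) or the shells (SAP 17.1), plans a number or percentage of BLQ values, and SAP 15 plans no figures. SAP 9 also leaves open whether the two thirds is counted per cell, per column or per agent, so two programmers could produce different primary tables from the same text.

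The controls are where this matters most. Protocol 3.1 says GdCA-naïve patients "will be included as controls for any background concentration of Gd in bone, e.g. from the environment", and they are the cells most likely to exceed one third BLQ. A blank control cell leaves the agent summaries with no tabulated background, although a high BLQ proportion among controls is itself the background result. The reader would have to rebuild the median, range and BLQ count from listings.

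**Working it through.** **Enrolment figures (the only sample-size figures stated; there is no power calculation).** From SAP 8.6: 6 × (5 + 5 + 3) + 2 × 3 = 84 exposed, and 84 + 15 controls = 99. Both reproduce.

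**Cell sizes (SAP 8.2.2 and 8.6).** Agent by renal function, single and multiple doses together:
- normal function: 5 + (3 to 5) = 8–10
- impaired, gadobutrol and gadoteric acid: 5 + (3 to 5) = 8–10
- impaired, the other four agents: 5 + (0 to 5) = 5–10

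Controls: 5 normal and about 10 impaired, 15 in total.

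**Thresholds.** Let K be the number of quantified values in a cell of n. The rule needs K ≥ ceil(2n/3): 4 of 5, 6 of 8, 7 of 10, 10 of 15. The median is measured (both central values if n is even) when K is at least 3, 5, 6 and 8 respectively. The maximum is measured when K ≥ 1.

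Example at n=5: two BLQ values (40%) trigger the rule, yet the 3rd, 4th and 5th ordered values are all measured.

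**Chance that a cell is withheld although its median was measured.** K is binomial with probability p of being quantifiable. The documents give no BLQ rate, so p is an assumption. The event is K=3 (n=5), K=5 (n=8), K=6 (n=10), K=8 or 9 (n=15).

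| p | n=5 | n=8 | n=10 | n=15 | either control column |
|---|---|---|---|---|---|
| 0.5 | 0.312 | 0.219 | 0.205 | 0.349 | 0.453 |
| 0.6 | 0.346 | 0.279 | 0.251 | 0.384 | 0.510 |
| 0.7 | 0.309 | 0.254 | 0.200 | 0.228 | 0.447 |
| 0.8 | 0.205 | 0.147 | 0.088 | 0.057 | 0.275 |

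The last column is 1 − (1 − P5)(1 − P10), taking the two control columns (5 and 10) as independent with the same p, for one tissue. At p=0.6: 1 − 0.654 × 0.749 = 0.510.

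Below 50% quantifiable these chances fall. At p = 0.4/0.3/0.2 they are 0.230/0.132/0.051 for n=5 and 0.111/0.037/0.006 for n=10. For either control column they are 0.316/0.164/0.056.

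**Chance that a cell is withheld although its maximum was measured**, P(1 ≤ K < required):

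| p | n=5 | n=8 | n=10 |
|---|---|---|---|
| 0.2 | 0.666 | 0.831 | 0.892 |
| 0.3 | 0.801 | 0.931 | 0.961 |
| 0.4 | 0.835 | 0.933 | 0.939 |
| 0.5 | 0.781 | 0.852 | 0.827 |
| 0.6 | 0.653 | 0.684 | 0.618 |
| 0.7 | 0.469 | 0.448 | 0.350 |

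**Chance that a control column prints, by assumed true level.** SAP 8.5 implies an LLOQ of 2 × 0.025 = 0.05. Assume lognormal values with geometric mean GM and geometric SD (GSD) 1.5–3. Then p = Φ(ln(GM/LLOQ)/ln GSD), and the chance of printing is P(K ≥ required).

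| GM/LLOQ | n=5 | n=10 |
|---|---|---|
| 0.5 | 0.00–0.02 | 0.00–0.01 |
| 1 | 0.19 | 0.17 |
| 1.5 | 0.42–0.82 | 0.50–0.94 |
| 2 | 0.60–0.98 | 0.74–1.00 |
| 4 | 0.91–1.00 | 0.99–1.00 |

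**Where the documents place the levels.** Protocol 1.1 reports less than 0.1 µg/g dry weight in untreated cranial bone. If the LLOQ is 0.05 µg/g on the same basis, that is below 0.1/0.05 = 2 × LLOQ. Exposed cranial bone at 1–21 days was 0.1–0.8 µg/g, or 2–16 × LLOQ, so many agent cells may print. In this study the interval from dosing is at least one month with no upper limit.

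**The case against.** **The SAP may mean only mean-type statistics.** Its reason names point estimates, it says should rather than will, and the shells ask for all SAP 8.1 statistics. That reading is plausible, and the white paper SAP 9 cites is not available to settle it. But the SAP does not state it, and the shell instruction does not address cells below the threshold. On either reading no BLQ count is planned.

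**N is recoverable.** The PPS requires Gd data in both bone types and skin, the demographic tables cover the PPS by treatment and renal function, and Table 14.5.1 counts samples taken. This stands: the loss of N is the smallest part of the problem. It does not restore the median, range or BLQ count.

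**The median figures peak in the range shown.** Below 50% quantifiable the chance of losing a measured median falls to 0.05–0.23 at n=5. This also stands. But the chance of losing a measured maximum is then 0.67–0.96 for n=5–10, and a median printed as <LLOQ beside a BLQ count is what a reader needs from a control group.

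**The evidence on background is thin.** Protocol 3.1 also says Gd has been found in bone of unexposed patients. The figure below 0.1 is an upper bound in cranial bone per dry weight, and the SAP gives µg/g without a wet or dry basis. This is fair, and the level-based figures are conditional for that reason.

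**The information is available elsewhere.** A blank cell tells the reader that more than a third of values were BLQ, the interim analysis covered the naïve subjects, and the listings hold individual values. All true, but a blank does not say how many were BLQ, whether the interim tables applied this rule is not visible, and a listing is not a primary summary. A total control column (n=15) is subject to the same rule.

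**Conclusion.** The concern holds and should be fixed. As written, SAP 9 removes statistics from the primary tables that its own bias argument does not reach, and puts no BLQ count in their place. That textual gap does not depend on any assumed rate.

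How often it bites depends on the unknown BLQ rate. At 50–70% quantifiable, a measured median is withheld with probability 0.31–0.35 (n=5), 0.22–0.28 (n=8), 0.20–0.25 (n=10) and 0.23–0.38 (n=15). At 80% it is 0.21, 0.15, 0.09 and 0.06. If typical levels reach 4 × LLOQ, nearly every cell prints and little is lost. If control background sits at the LLOQ, a control column prints less than one time in five. These figures assume independent values with a common p and, for the level-based ones, lognormal data and an LLOQ of 0.05 µg/g on the same basis as the cited bone values.

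No data are lost and no test is affected. What is at risk is the tabulated primary result, chiefly for controls.

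**What to change.** 1. In SAP 9, limit the 2/3 rule to the arithmetic and geometric mean, SD, geometric SD and CV, and state that it is applied per table cell.
2. In every Gd cell, controls included, always print N, n (%) BLQ, minimum, median and maximum, showing `<LLOQ` where that order statistic is BLQ. If N is even and the two central values straddle the LLOQ, print both.
3. In SAP 8.5, confine LLOQ/2 substitution to the mean-type statistics, so that 0.025 never appears as a measured minimum or median. State the LLOQ with its unit.
4. Add the rule to the changes listed in SAP 10, which records the LLOQ/2 substitution (10.1) but not this threshold. This is a minor cross-reference.

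The cost is a few sentences in SAP 8.5, 9 and 10, one extra row in the Gd tables and little programming. The tables become slightly longer and may differ in layout from the interim ones. The SAP's protection against biased means is kept.

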9.1 Subject Disposition

Subject disposition will be tabulated with number and percentages of subjects screened, enrolled, completed according to the protocol, number of surgeries, lost to follow-up or discontinued prematurely. The subjects who prematurely discontinued the study and the reasons for their discontinuation will be presented. Screening failures will be excluded from the analysis but listed in subject data listings.

9.2 Demographic Data and Baseline Characteristics

All Demographic data and baseline characteristics will be displayed for the SAF, FAS and PPS (see definition 8.3).

Demographic data and baseline characteristics will be analyzed using descriptive statistics in summary (mean, SD, median, min and max) or frequency (number and percentage) tables. The following parameters will be analyzed:

- Gender
- Age (years)
- Height (cm)
- Weight (kg)
- Historical use of gadolinium based contrast agent (GBCA)
- Diagnosis of qualifying study indication (affected joint, diagnosis, duration, severity of diagnosis)

